14. Psychiatric/Behavioral	Dementia, depression, anxiety, agitation, psychosis		
	TOTAL		

Each system is rated as follows:

- 0 = NONE: No impairment to that organ/system
- 1 = MILD: Impairment does not interfere with normal activity; treatment may or may not be required; prognosis is excellent. (Examples could be skin lesions, hernias, or hemorrhoids)
- 2 = MODERATE: Impairment interferes with normal activity; treatment is needed; prognosis is good. (Examples could be gallstones, diabetes, or fractures)
- 3 = SEVERE: Impairment is disabling; treatment is urgently needed; prognosis is guarded. (Examples could be resectable carcinoma, pulmonary emphysema, or congestive heart failure)
- 4 = EXTREMELY SEVERE: Impairment is life threatening; treatment is urgent or of no avail; prognosis is grave. (Examples could be myocardial infarction, cerebrovascular accident, gastrointestinal bleeding, or embolus)

Appendix B – ECOG Performance Status

Grade	ECOG
0	Fully active, able to carry on all pre-disease performance without restriction
1	Restricted in physically strenuous activity but ambulatory and able to carry out work of a light or sedentary nature, e.g., light house work, office work
2	Ambulatory and capable of all selfcare but unable to carry out any work activities. Up and about more than 50% of waking hours
3	Capable of only limited selfcare, confined to bed or chair more than 50% of waking hours
4	Completely disabled. Cannot carry on any selfcare. Totally confined to bed or chair
5	Dead

Appendix C – Concomitant Medications – Prohibited or Cautionary Use

Note: As these lists are constantly evolving, if a medication is incorrectly documented as prohibited in this protocol, documentation from the site pharmacist to the contrary will be acceptable for the purposes of registration.

CYP3A4 inducers (prohibited): Carbamezepine Ethosuximide Griseofulvin Phenytoin Primidone Progesterone Rifabutin Rifampin Nafcillin Nelfinavir Nevirapine Oxcarbazepine Phenobarbital Phenylbutazone Rofecoxib St John's wort Sulfadimidine Sulfinpyrazone Troglitazone High Risk QTc Prolonging Agents (cautionary use): Note: The following medications are only prohibited in the case that a patient develops known QTc prolongation on study. Amiodarone Flecainide Anagrelide Halofantrine Arsenic trioxide Haloperidol Azithromycin Ibutilide Chloroquine Methadone Chlorpromazine Moxifloxacin Citalopram Ondansetron** Clarithromycin Pentamidine Disopyramide Pimozide Dofetilide Quinidine Dronedarone Sevoflurane Droperidol Sotalol Erythromycin Thioridazine Escitalopram Vandetanib

**Will be given as pre-medication for romidepsin unless patient develops known QTc prolongation

IRB #: STU00097620-CR0005 Approved by NU IRB for use on or after 3/21/2022 through 3/20/2023.

Study Number: NU 14H04 RV-CL-PTCL-PI-003974

Appendix D – Creatinine Clearance

The following equations should be used to calculate creatinine clearance.

For males:

Creatinine Clearance =

(140 - age [years] x weight [kg]) 72 x (serum creatinine [mg/dL])

OR

(140-age [years] x weight [kg]) 0.81 x (serum creatinine [µmol/L])

For females:

Creatinine Clearance = 0.85 (140-age [years] x weight [kg]) 72 x (serum creatinine [mg/dL])

OR

0.85 (140-age [years] x weight [kg]) 0.81 x (serum creatinine [µmol/L])

Source: Cockcroft DW, Gault MH. Prediction of creatinine clearance from serum creatinine. Nephron 1976;16(1):31-41.

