3.1 Inclusion Criteria

- 3.1.1 Histologically confirmed diagnosis of PTCL (using the most recent edition of the WHO Classification of Tumors of Hematopoietic and Lymphoid Tissues as guidance) including:
 - Anaplastic large cell lymphoma, ALK-negative
 - Angioimmunoblastic T-cell lymphoma
 - Enteropathy-type T-cell lymphoma
 - Hepatosplenic γδ T-cell lymphoma
 - Peripheral T-cell lymphoma, unspecified (NOS)
 - Transformed mycosis fungoides
 - Subcutaneous panniculitis-like T-cell lymphoma

• Adult T-cell lymphoma/leukemia (ATLL) in need of systemic therapy. NOTE: Patients with adequate archived (well-preserved, formalin-fixed) biopsy tissue remaining will be required to submit a portion for exploratory studies. This is not optional if tissue is available; however, lack of adequate tissue for exploratory studies will not preclude patients from participating.

- 3.1.2 Patients must have bi-dimensionally measurable disease (≥1 cm) by CT imaging. NOTE: Patients with marrow-only disease are eligible; response for these patients will be assessed by repeat bone marrow biopsy.
- 3.1.3 Patients must fit into one of the following categories:
 - Age ≥ 18 years to < 60 years with a cumulative illness rating scale (CIRS) score ≥ 6 OR deemed ineligible for cytotoxic chemotherapy by the treating investigator (see Appendix A for CIRS scoring[42])
 - ≥ 60 years
- 3.1.4 Patients must have adequate organ and marrow function (documented within 14 days prior to registration) as outlined below:

System Laboratory Values				
Hematologic				
ANC	≥ 750/mcl			
Hemoglobin	≥ 8 g/dI			
Platelets	≥ 50,000/mcl			
Hepatic				
Total Bilirubin	≤ 2x upper limit normal (ULN)			
AST (SGOT) and ALT (SPGT)	≤ 3x ULN			
Renal				
Creatinine Clearance	≥ 30 mL/min			
See Appendix D to reference the Cockgroft-Gault equation for				
calculating creatinine clearance.				

- 3.1.5 Patients must have an ECOG performance status ≤ 2 (see Appendix B).
- 3.1.6 All patients must agree to use effective contraception while on study, and all patients must agree to undergo counseling sessions every 28 days about pregnancy precautions and risks of fetal exposure.

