4.1.3 Treatment regimen & supportive therapies

Table 1 below summarizes the treatment regimen and recommended supportive therapies for patients on this trial.

Agent	Recommended Premedications ¹	Dose	Route	Schedule ³	Duration				
Domidencin ²	30 min prior: $5-HT3 \text{ receptor}$ antagonist4 Dexamethasone 10 10 mg/m^2 IVDays 1, 8, 1 year or 								
Romidepsin-	antagonist⁴ Dexamethasone 10 mg IVPB	14 mg/m²	IV	Days 1, 8, 15	1 year or until POD				
LenalidomideNone25 mg5poDaily Days 1-2151 year or until POD ¹ Premedication protocol is for romidepsin infusions and includes recommended agents									
¹ Premedication and trea ² The parameters pati ³ Each cycle will and with ⁴ The recommen ⁵ The dose and s severe renal imp	protocol is for romidepsin doses; similar alternate r ting investigator. s specified in the shaded ent tolerates 2 or more cy be 28 days; romidepsin ir hin +3 days of days 8 and ded agent/dose is Zofran schedule of lenalidomide s pairment, as detailed in Ta	infusions medication boxes repr ccles (6 tot nfusions sh 15. 16 mg IVF should be able 1b be	and incluc s may be resent opt al doses) nould occu PB or equi adjusted f low.	les recommend given at the dis ional dose incr at 10 mg/m ² ur within ±3 day ivalent. or patients with	ded agents scretion of the ease if rs of day 1, moderate or				

-	Table	1a:	Treatment	Regimen
---	-------	-----	-----------	---------

Table 1b: Lenalidomide Dose Adjustments for Patients with Renal Impairment

Category	Renal Function	Dose and Schedule
Moderate	Creatinine clearance 30-60 ml/min ¹	10 mg daily (Days 1-21)
Severe	Creatinine clearance < 30 ml/min	15 mg every other day (Days 1, 3, 5, 7, 9,
	(not requiring dialysis) ¹	11, 13, 15, 17, 19, and 21)

¹ Creatinine clearance (CrCl) will be measured and calculated prior to initiating each cycle as described in the Study Procedures Table in Section 5.0. (Refer to Appendix D for instructions on calculating CrCl). The dose of lenalidomide will be adjusted per Table 1b. Any questions regarding dose calculations/adjustments should be directed to the Lead Pl.

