- ²⁰ Creatinine clearance will be measured and calculated prior to initiating each cycle (Refer to Appendix D for instructions on calculating creatinine clearance). The dose of lenalidomide will be adjusted per Table 1b. Any questions regarding dose calculations/adjustments should be directed to the Lead PI. Refer to Section 4.1.3 for additional information.

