11.4 Registration Procedures

Patients may not begin protocol treatment prior to registration. All patient registrations will be registered centrally through the Clinical Trials Office (CTO) at Northwestern University before enrollment to study. In order for registrations to be processed efficiently, staff are asked to inform the QAM of date and time that by which the patient will need to be registered. Please contact the assigned Quality Assurance Monitor (QAM) or email the QA Department ([contact]) for questions regarding patient registration.

Prior to registration, eligibility criteria must be confirmed by the assigned QAM. The study coordinator will screen all subjects for potential registration via the web-based application NOTIS (Northwestern Oncology Trial Information System), which is available at: https://notis.nubic.northwestern.edu. Please note that a username and password is required to use this program, and will be provided during site activation prior to training on the NOTIS system.

BEFORE a patient can be treated on study, please complete and submit the following items to confirm eligibility and receive an identification number:

- Patient's signed and dated informed consent form (upload to NOTIS and keep original hard copy in a secure location/study chart)
- Eligibility checklist (signed and dated by the treating physician upload to NOTIS)
- Eligibility eCRF (complete in NOTIS)
- Copy of the pathology report (upload to NOTIS)

Training on eCRF completion will be provided at the time of site activation. Please refer to the eCRF demonstration videos on the CTO website for additional instructions on registering a patient.

The QAM will review the registration, register the patient, assign a subject identification number, and send a confirmation of registration to study personnel. Registration will then be complete and the patient may begin study treatment.

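### Appendix D closes the bracket in the wrong place in all four creatinine clearance expressions, so each, taken literally, gives a negative clearance for any adult

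*Combined protocol and SAP*

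**What the plan says.** Appendix D opens with an instruction: "The following equations should be used to calculate creatinine clearance". It then gives four expressions. The male mg/dL numerator reads "140 - age [years] x weight [kg", and its round bracket closes only after the weight term. The male µmol/L line has the same layout over its divisor: "140-age [years] x weight [kg]) 0.81 x (serum creatinine [µmol/L". Both female lines put the sex factor in front of the same single bracket: "0.85 (140-age [years] x weight [kg". The appendix ends with a citation of the source article for the Cockcroft-Gault equation.

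Three places send sites to this appendix:

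- Section 3.1.4 requires a clearance of at least 30 mL/min and adds: "See Appendix D to reference the Cockgroft-Gault equation for" calculating it.
- Table 1b, footnote 1 (Section 4.1.3) bases the lenalidomide dose on it. A clearance of 30-60 mL/min means 10 mg daily on days 1-21; below 30 means 15 mg every other day.
- Table 4, footnote 20 (Section 5.0) repeats the requirement: "Creatinine clearance will be measured and calculated prior to initiating each cycle".

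No other section prints the equation.

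**The concern.** Multiplication comes before subtraction, so a bracket that closes after weight makes the numerator 140 − (age × weight). For any adult the product of age and weight is far above 140, so the numerator is negative. The sensible quantity is (140 − age) × weight, with the bracket closed after age.

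The text is operative. It decides whether a patient meets 3.1.4 and, before every cycle, which lenalidomide dose applies. Followed to the letter, no patient would be eligible and every patient would fall in the severe row of Table 1b.

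**Working it through.** The plan gives no worked clearance, so there is no figure of its own to reproduce. The check evaluates the expressions as printed and again with the bracket moved.

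**Inputs from the documents.** Appendix D: the single-bracket numerator, divisors 72 × creatinine (mg/dL) and 0.81 × creatinine (µmol/L), and the female factor 0.85. Section 3.1.3: minimum age 18. Section 3.1.4: limit of 30 mL/min. Section 4.1.2 and Table 1b: lenalidomide is adjusted below 60 mL/min.

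**Assumed inputs.** The patient values are illustrative. The conversion 1 mg/dL = 88.4 µmol/L is not in the documents; it is used only for the µmol/L lines.

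**Formulas (mg/dL, male; multiply by 0.85 for female).**

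- As printed: (140 − age × weight) / (72 × creatinine)
- Bracket moved: (140 − age) × weight / (72 × creatinine)

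**Worked case: 65 years, 70 kg, 1.0 mg/dL, male.**

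- As printed: (140 − 65 × 70) / 72 = (140 − 4550) / 72 = −4410 / 72 = −61.25
- Bracket moved: (140 − 65) × 70 / 72 = 5250 / 72 = 72.92

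**Further cases (mL/min).**

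| Age, weight, creatinine | Male, printed | Male, moved | Female, printed | Female, moved |
|---|---|---|---|---|
| 18 y, 40 kg, 1.0 mg/dL | −8.06 | 67.78 | −6.85 | 57.61 |
| 65 y, 70 kg, 1.0 mg/dL | −61.25 | 72.92 | −52.06 | 61.98 |
| 75 y, 60 kg, 1.5 mg/dL | −40.37 | 36.11 | −34.31 | 30.69 |
| 80 y, 50 kg, 1.5 mg/dL | −35.74 | 27.78 | −30.38 | 23.61 |

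With the bracket moved, the results separate patients in the way the protocol needs: the 65-year-olds are above 60, the 75-year-olds fall in the 30-60 band, and the 80-year-olds are below the eligibility limit. As printed, all are negative.

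**µmol/L lines.** For the 65-year-old at 88.4 µmol/L the divisor is 0.81 × 88.4 = 71.604. Male: −4410 / 71.604 = −61.59 as printed, against 5250 / 71.604 = 73.32. Female: −52.35 against 62.32. Also 72 / 88.4 = 0.814, so the two divisors agree with each other and show no second fault.

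**When is the printed result positive?** Only if age × weight is below 140, that is, weight below 140 / age: 140 / 18 = 7.78 kg at 18 years, 140 / 60 = 2.33 kg at 60, and 140 / 80 = 1.75 kg at 80. The sign does not depend on creatinine, sex or units, so the result is negative for every eligible patient.

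**The case against.** The strongest reply is that this is a typographical slip with no demonstrated consequence. The most dangerous formula errors give a plausible wrong number. This one gives an impossible number, so it would be noticed at first use. The documents name the intended equation in Section 3.1.4 and cite its source in Appendix D. There are also checks: Section 11.4 states, "Prior to registration, eligibility criteria must be confirmed by the assigned QAM", and Table 1b footnote 1 and Table 4 footnote 20 give an escalation route: "Any questions regarding dose calculations/adjustments should be directed to the" lead investigator. All of this stands, and it is why the point ranks low.

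Two further points deserve an answer. First, the text was read from PDF and its fraction bars are gone, so a lost inner bracket cannot be fully excluded. It is unlikely, because the same placement occurs four times while the neighbouring brackets around creatinine and the units are intact. Looking at the PDF settles it. Second, the documents do not print the correct form. They prove that the printed form is impossible; that (140 − age) × weight is what was meant relies on recognising the named equation.

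The timing argument, that Appendix D came in with Amendment 7 in July 2018 and the current version is Amendment 11 of November 2021, reduces the yield of a correction but does not make the text right. Appendix E records that Amendment 9 corrected a reversed inequality in this same clearance criterion, so the sponsor has already treated an error of this kind as worth an entry.

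**Conclusion.** The concern holds, as a notation error in operative text. All four expressions in Appendix D are wrong as written and negative for every eligible patient: for example −61.25 instead of 72.92 mL/min for the 65-year-old man, and −35.74 instead of 27.78 for the 80-year-old man.

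The effect in practice should be small. Actual misdosing, wrongful exclusion or divergence between sites is unlikely and is not asserted. The sample size, endpoints and analysis are untouched. It is something for the sponsor to consider correcting, not a threat to the trial.

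The sign result rests on the bracket placement being as in the source PDF. The corrected values rest on the bracket being the only fault, which the agreement of the two divisors supports, and on illustrative patient values.

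**What to change.** First confirm the bracket placement in the source PDF. Then, in the next amendment, write all four numerators as (140 − age [years]) × weight [kg], keeping the 0.85 factor for females and the 72 and 0.81 divisors. One worked example under the equations would be a useful but optional safeguard. The cost is an editorial change of one bracket in four lines and an entry in Appendix E, with no change to design, eligibility limits, dose bands or analysis.

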Appendix E – Protocol History of Changes

Original Version Submitted to IRB & FDA – June 24, 2014			
Amondment 4 Changes Required During IRR & ERA Review Contember 2, 2014			
Amendment 1 – Changes Required During IRB & FDA Review – September 3, 2014			
Section(s) Affected	Prior Version	Amendment 1 Changes	Rationale
Cover-page	IND# listed as pending	IND# updated to 123,818	Administrative
Throughout	n/a	Corrects minor spelling and/or grammatical errors.	Administrative
Study Summary	Summary of statistical methodology appeared to suggest the study was designed to demonstrate superior response rates compared to historical controls. Percentages and accrual goals didn't clearly align with other sections of the protocol.	Revised summary to more accurately reflect the design and numbers as described in the full statistical section.	Change requested by IRB during initial review.
1.4 (Study Rationale), 7.4 (Stopping Rules)	Accrual goal not clear (35 vs. 32) and criteria for early stopping incorrectly listed as 5 of 11 in the first stage.	Clarified that up to 35 patients may be enrolled to achieve 32 evaluable; also corrected early stopping criteria to indicate that if 6 or fewer of the first 12 patients had a response, the study would be closed to further accrual.	Change requested by both FDA and IRB during initial review.
1.4 (Study Rationale), 2.1 (Primary Objective & Endpoint), 10.1 (Primary Endpoint & Sample Size Calculations)	Not clear what response assessment time point would be used for the purposes of evaluating early stopping.	Clarifies that response at the 3 month time point (after cycle 3) will be used to determine whether or not the trial meets early stopping criteria for efficacy.	Clarification requested by FDA during initial review.
3.2 (Exclusion Criteria)	Excluded patients with a QT interval > 500 msec.	Revised to exclude patients with a QT interval > 480 msec.	Change requested by FDA during initial review.
4.0 (Treatment Plan), 4.4 (Duration of Therapy)	n/a	Adds clarification that patients who do not achieve a response of PR should only remain on treatment up to 1 year if they have SD (not PD) AND if no other options are available that would offer a more favorable risk/benefit ratio.	Clarification requested by FDA during initial review.
4.1.1 (Romidepsin Administration), 5.0 – Table 4 (Time & Events)	Stated that patients who tolerated the regimen for 2 cycles (6 doses) could be escalated to 14 mg/m ² at the investigator's discretion.	Revises this to allow escalation to the 14 mg/m ² dose only if the patient has not achieved a CR and has not experienced any grade 3-4 AEs.	Safety change required by FDA during initial review.
4.1.2 (Lenalidomide Administration), 4.1.3	n/a	Adds different dosing for patients with moderate or	Safety change required by FDA during initial review.

(Table 1b)		severe renal impairment	
		(creatinine clearance < 60 ml/min) who are enrolled on	
		the trial.	
		Changed to require	
4.2 (Toxinition Doning	Grade 3-4 non-	resolution to \leq Grade 1;	
4.2 (TOXICILIES, DOSING	required to resolve to <	recurrence of a grade 4	Safety change required by
Modifications)	Grade 2 before further	non-hematologic toxicity	FDA during initial review.
	treatment.	must result in removal from	
		trial therapy.	
		Adds "& Early Withdrawal"	
		to the section title and	
4.4 (Duration of		of the listed events will	Clarification requested by FDA
Therapy)	n/a	result in early withdrawal	during initial review.
(inclup)		from study treatment or (in	
		some cases) the study as a	
		whole.	
		New section added to clarify	
4.7 (Suppopulation of		monitoring and the authority	Clarification requested by EDA
4.7 (Suspension of	n/a	Committee to suspend	during initial review
		accrual in the event of	during million review.
		excessive toxicity.	
		Changed to require CBC	
5.0 - Table 4 Time &	CBC required at	weekly for the first 2 cycles,	Safety change required by
Events	baseline and once per	then every other week for	FDA during initial review.
Literite	cycle.	cycles 3-6, then at the start	
		Of each cycle inereafter.	
		natients (enrolled in the first	
		stage) who demonstrate	
		clinical benefit (SD or	
7.4 (Stopping Rules)	n/a	better) may continue to	during initial roview
		receive study treatment up	during million review.
		to 1 year in accordance with	
		the duration of therapy	
Amendmen	t 2 – Additional Changes I	Required During FDA Review	- October 3, 2014
Section(s) Affected	Prior Version	Amendment 2 Changes	Rationale
4.3.2 (Permitted	Stated that leukocvte	Removes this statement.	Safety change required by
Conmeds)	growth factors may be		FDA during initial review.
,	given concurrently with		-
	protocol treatment.		
11.0 (Study	n/a	Adds new section 11.11 to	Added per FDA requirement
ivianagement)		ritoria that will trigger	ouring initial review.
		automatic suspension of	
		study accrual.	
	·		
Amendment	3 – Additional Changes Re	equired During FDA Review –	December 17, 2014
Section(s) Affected	Prior Version	Amendment 3 Changes	Rationale

11.11 (Criteria for	Definition of excessive	Revises this to rule to	Revised per FDA requirement
Suspension of Accrual)	toxicity included >20% of any single grade 4 toxicity after at least 10 subjects are treated, or more that 30% grade 4-5 toxicity with at least 90% probability.	define the toxicity event as any grade \geq 4 neutropenia, grade \geq 4 thrombocytopenia, or grade \geq 3 organ toxicity at least possibly related to the study regimen, and limits the toxicity events to no more than 20% with 80% posterior probability.	during review of clinical hold.

Amendment 4 – Changes due to Transition of PI – November 16, 2015			
Section(s) Affected	Prior Version	Amendment 4 Changes	Rationale
Cover Page	[name] listed as PI and IND Holder	Removes [name] and adds [name] as PI and IND Holder	Administrative – change in faculty
Cover Page	Listed Yale Cancer Center as a participating site	Removes Yale and adds Ohio State University as a participating site	Administrative
Signature Page	Includes signature page	Removes signature page	Aligns with new NU protocol template
Schema, Study Procedures (Sec 5.0, Footnote 2, 11)	Response assessment included diagnostic CT with contrast	CT's can be performed with or without contrast	Revised per discussion with PI
Patient Eligibility (Sec 3.0)	Stated that study will be conducted in NMDTI	Removes language specifying NMDTI as location for study procedures	Allows flexibility to avoid deviations
	3.1.1 - Lists "extranodal NK/T-cell lymphoma, nasal type" as included type of PTCL	3.1.1 – removes "extranodal NK/T-cell lymphoma, nasal type" as type of PTCL	Per PI discussion
Inclusion Criteria (Sec 3.1.1 & 3.1.6)	3.1.1 - Included note specifying markers to be present for eligibility	3.1.1 – removes note for biomarkers	Per PI discussion – allows for less stringent eligibility
	3.1.6 - Referred to attached for REMS program	3.1.6 – removes reference to REMS program	Referenced elsewhere
	3.2.2 – Note listed twice	3.2.2 – Removes Second Note	Redundant
Exclusion Criteria (Sec 3.2.2, 3.2.4, 3.2.6	3.2.4 – "Patients who received prior exposure to"	3.2.4 – "Patients who have received"	Revised for clarity
	3.2.6 – "Patients who have known CNS"	3.2.6 – "Patients with known CNS…"	Revised for clarity
Study Procedures (Sec	"Each Cycle" column	"Day 1 of Each Cycle"	Revised for clarity
5.0)	n/a	Added column for Day 8 & 15 of cycles	Revised for clarity

	Pregnancy test required "each cycle"	Footnote 18 – Pregnancy test only required D15 of each cycle	Revised for clarity
	Footnote 5 – ECG required "at baseline"	Footnote 5 – ECG required "within 28 days of registration"	Revised for clarity
	Footnote 8 – required physical exam and medical history to be within 14 days	Footnote 8 – requires only Chemistry and Hematology to be within 14 days	Per PI discussion – allows appropriate flexibility for procedure
	Footnote 9 – allowed for labs to be used for C1D1 if within 7 days	Footnote 9 – removes language, requiring new labs for C1D1	Per PI discussion – labs should be checked for safety
	Footnote 16	Footnote 16 – Bone marrow biopsy "within 90 days of registration"	Per PI discussion – allows appropriate flexibility for procedure
Romidepsin Availability & Drug Ordering (Sec 8.1.6)	"Please see separately attached Appendix F for details"	"Romidepsin order form is available at the NOTIS website – contact QA for any issues/concerns"	Administrative – allows for changes in order form without amending protocol
Lenalidomide Availability (Sec 8.2.7)	n/a	Adds instructions for ordering Revlimid through Biologics, Inc.	Administrative – study coordinator request

Amendment 5 – June 16, 2016			
Section(s) Affected	Prior Version	Amendment 5 Changes	Rationale
	 Listed Ohio State University 	Removed Ohio State University	Administrative – change in affiliate sites participating
Cover Page	 Had incorrect address for Cornell Medical College 	Added correct address for Cornell Medical College	
Study Summary page	• N/A	Updated Participating sites	Administrative – change in affiliate sites participating
	Amendmer	nt 6 – March 10, 2017	
Section(s) Affected	Prior Version	Amendment 6 Changes	Rationale
Cover Page; Study	Included University of	Removes University of	Administrative
Summary; 3.0 (Patient Eligibility)	Washington as an affiliate site	Washington from affiliates	
Study Schema; 3.1.1	n/a	Adds adult T-cell lymphoma/	Expansion of eligibility to
(Inclusion Criteria);		leukemia (ATLL) as eligible	increase enrollment
3.2.1 (Exclusion		PTCL subtype (removes	
Criteria)	Included chart title and	from excluded subtypes)	
Study Summary	protocol number in summary	protocol number	protocol template
3.2.2 (Exclusion	Corticosteroids were	Adds clarification that	Clarification – prior language
Criteria);	listed as being generally	corticosteroids are permitted	was unclear whether
4.3.2 (Permitted	excluded in eligibility	on study to treat any	corticosteroids of any type

Concomitant	criteria, and were not	condition other than PTCL.	were excluded, rather than
Medications);	listed in concomitant	Corticosteroids for PTCL are	steroids to treat PTCL
Concomitant	medications	treatment, but are permitted	
Medications)		prior to treatment for 10 or	
	Evoluted chamatharapy	fewer days	Clarification for simplicity
3.2.3, 3.2.10 (Exclusion	and high QT "within 4	high QT"≤ 28 days" prior to	Clarification for simplicity
Criteria)	weeks" prior to	registration	
326 (Exclusion	registration	Expands CNS (central	Clarification
Criteria)		nervous system)	Clamouton
4.0 (Treatment Plan);	Allowed a cycle window	Allows cycle window of ±3	Allows greater flexibility for
4.1.3 (Treatment regimen & supportive	of ±1 business day	days	VISItS
therapies); 5.0 (Study			
Procedures #10)	Detiente mou he	Detionto may be appolated	Clarification only a drug
4.4.4 (Demidensin)	escalated to 14mg/m ²	to 14mg/m ² romidepsin if	related AE would preclude
	romidepsin if they don't	they don't have drug-	patients from escalating in
4 1 1 (Romidensin) [.]	Recommended pre-	related grade 3-4 AE's Pre-medications are listed	dose An equivalent dose is
4.1.3 (Treatment	medications are Zofran	as Zofran 16mg and	recommended (rather than
regimen & supportive	16mg and	dexamethasone 10mg (or	saying "similar agent", which
(Recommended	(or similar agents)	equivalent)	avoid higher doses that may
Concomitant			prolong QTc (e.g. kytril > 2mg)
Medications Include);	"Romidensin infusions	"Romidensin infusions	Allows greater flexibility on day
4.1.3 (Treatment	should occur within 1	should occur within ±3 days	1 (to align with cycle windows),
therapies); 5.0 (Study	business day of days 1,	of day 1, and within +3 days	but maintains appropriate
Procedures #10,15)	8, and 15	or days 8 and 15.	window between infusions.
	Table 1b: "Dose	Table 1b: "Lenalidomide	Clarification – previously
113 (Treatmont	Adjustments"	Dose Adjustments"	unclear which drug was to be
regimen & supportive	Table 1b: severe renal	Table 1b: severe renal	Discrepancy – CrCl = 30
therapies);	impairment defined as	impairment defined as CrCl	previously fell into both
	CrCl ≤ 30	< 30	moderate and severe categories
4.2 (Toxicities, Dosing	CTCAE v4.0	CTCAE v4.03	Administrative update
Delays, and Dose			
(Toxicity Endpoints);			
7.2.2 (Severity of AE's)			
4.2 (Toxicities Dosing	Both study drugs were to be delayed or modified in	Adds that toxicity should be attributed to one study drug	Clarification – clinically, if one study drug is not related to an
Delays, and Dose	the case of a drug-	whenever possible.	AE, it should be continued as
Modifications); 7.2.5	related toxicity	Modifications/delays may	normal
(הוווטעווטווס)		caused toxicity, or both.	
4.2 (Toxicities, Dosina	For any Grade 3-4	Adds exceptions for Grade	Aligns more closely with
Delays, and Dose	toxicity, lenalidomide	3-4 AE's where the dose of lenalidomide should be	standard practice
Modifications)	the same dose upon	reduced by 5mg (G3 rash or	

	resolution of the first occurrence	neuropathy, G3 or 4 tumor lysis syndrome or tumor flare) or discontinued (G4	
		rash or neuropathy, or any grade blistering rash)	
	Romidepsin dose could be reduced from 10mg/m ² to 7mg/m ²	Changes dose reduction to 8mg/m ² (from 10mg/m ²)	To align with standard dosing
4.2.1 (Pregnancy)	n/a	Patients who become or are suspected to be pregnant while on study treatment must discontinue immediately. Refers to 7.2.6 for reporting requirements	Required Celgene language for pregnancy reporting and monitoring.
4.3.3 (Prohibited Concomitant	Referenced appendix E for list of CYP3A4 inducers	References appendix C and adds note that pharmacist list of prohibited CYP3A4 inducers will take priority over list in the protocol.	The list of CYP3A4 inducers is constantly evolving
Medications); Appendix C	QTc prolonging agents were strictly prohibited	QTc prolonging agents are only prohibited in patients who develop QTc prolongation on study	QTc prolonging agents are not a risk unless a patient already has prolonged QTc; patients are required to have QTc ≤ 480 msec before the study
	n/a	Adds 1 cycle = 28 days	Clarification
	n/a	Adds cycle window (±3 days)	Clarification
	#2: n/a	#2: CT's must be of chest, abdomen, pelvis; neck if clinically indicated, and with or without contrast	Clarification
	#11: n/a	#11: Adds window of ±7 days for CT's, and clarifies they can be with or without contrast	Clarification
5.0 (Study Procedures)	#13: n/a	#13: Adds windows for follow-up visits (±7 days for q3months and ±14 days for q6months)	Clarification
	#16: Bone marrow biopsy was to be done at baseline and as response assessment for patients with marrow only disease and as clinically indicated in other patients	#16: Bone marrow biopsy will be done at baseline if clinically indicated. In patients with known bone marrow involvement at baseline, a biopsy will be performed after the patient achieves a CR	Clarification – language was previously unclear
7.2.6 (Pregnancy); 7.2.7 (Overdose)	n/a	Adds reporting requirements for patients who become pregnant or have an overdose of study treatment. Pregnancy and pregnancy outcomes must be reported on Celgene-	Additional safety language required by Celgene

		specific forms, and	
		overdose must be reported	
		on case report forms.	
	n/a	Adds contact information	Clarification to align with
7.3.4 (Reporting to		(fax and email) for Celgene	Celgene protocol template
Celgene)		Drug Safety and additional	
	Defense and a dimen	reporting instructions	
8 1 6 (Availability 8	Referenced a drug	Removes contact details for	NOTIS should be used for
Drug Ordering)	fax and email for	references instructions in	amendments in case of
Drug Ordering)	ordering romidensin	NOTIS	changing instructions
11.5 (Data	Referred to Appendices	Removes references and	To align with current NU
Management &	for the DSMP and data	Appendix C & D, instead	protocol template and policies
Monitoring/Auditing);	submission guidelines	referencing the DSMP	
Appendix C; Appendix		hyperlink and NOTIS	
D			
	Amendments must be	Adds that amendments will	Broader language to cover all
	sent to the IRB for	be sent for review by "local,	required reviews and
11.7 (Amendments to	approval.	institutional, and	approvals.
the Protocol)		governmental regulatory	
		Celgene" Amendments will	
		also be sent to affiliates	
	All medications were	Clarifies that QTc	Clarification to align with 4.3.3
	listed as "not permitted"	prolonging agents are	5
	·	"cautionary"; also clarifies	
Appendix C		that ondansetron will be	
		used as a pre-medication	
		unless a patient develops	
		QIc prolongation	
	 		
	Amendme	nt 7 – July 25, 2018	
Section(s) Affected	Brier Version	Amondmont 7 Changes	Pationalo
Section(s) Affected		Changes creatining sutoff	
	Organ function listed a	Changes creatinine cutoff	To align with dose
		x = 10 Creatinine Clearance,	4 1 3 and standard of care
3 1 4 (Inclusion Criteria):		ml /min	criteria for lenalidomide
Appendix D		Adds Appendix D to	chiena for fertalidoffilde.
		provide the formula for	
		calculating Creatinine	
		Clearance	
	Patients must be free of	Adds that "free of prior	To clarify prior confusion as
3.1.8 (Inclusion Criteria)	any prior malignancies for	malignancies" is at the	to the definition of
	≥1 year	investigator's discretion.	malignancy free
	n/a	Excludes patients who are	To address clarification
		receiving concurrent	brought up by an affiliate
226 (Evolution Critoria)		minunosuppressive	sile. It is not clinically
3.2.0 (Exclusion Chiena)			
			medications with the study
			treatment.
4.2 (Toxicities, Dosing	n/a	Adds: "If study drug is	Clarification; there was
Delays, and Dose		delayed more than 21 days	previously no language
Madifications)		(1 treatment cycle)	about maximum length of

		treatment may be discontinued after discussion with the PL"	holding patients for toxicity.		
4.3.2 (Permitted Concomitant Medications)	n/a	Transfusions and growth factor are clarified to be permitted at physician discretion and per institutional guidelines	Clarification requested by affiliate site; transfusion and growth factor were not previously mentioned		
4.3.3 (Prohibited Concomitant Medications & Treatments)	Concurrent radiotherapy was generally prohibited	Adds a stipulation that radiotherapy is permitted to treat a single non-target lesion for symptom control	Clarification resulting from a clinical situation. Patients should be permitted to receive radiotherapy separate from the disease target lesions as it does not affect disease assessments or study endpoints		
4.6 (Patient Replacement); 4.7 (Suspension of Accrual); 7.3 (Expedited Reporting of SAEs) 11.10 (Publication Policy); 11.11 (Criteria for Suspension in Accrual)	Referenced Data Monitoring Committee (DMC)	Updates to reference Data and Safety Monitoring Committee (DSMC)	Administrative update to align with internal policies		
5.0 (Study Procedures, #8)	n/a	SAE's are to be collected from the time of consent until 30 days after treatment	Clarification for easier referencing to align with SAE timelines within the protocol		
7.2.3 (Serious Adverse Events)	SAE's were to be collected during the study and for 30 days after treatment	Adds that SAE's will be collected from the time of consent until 30 days after treatment	Clarification requested by affiliate site		
	Amendment SRC-approved of	t 8 – July 5, 2019 on December 6, 2019			
Section(s) Affected	Prior Version	Amendment 8 Changes	Rationale		
Cover Page	Listed [name] as the Biostatistician	Updates to [name] as the new Biostatistician	Administrative update to account for staffing change		
Cover Page and Throughout	Coordinating Center was listed as the Clinical Research Office (CRO) at Northwestern	Updates the name of the coordinating center to the Clinical Trials Office (CTO) at Northwestern	Administrative update to account for a change in the coordinating center's name; the coordinating center itself will remain the same.		
Study Summary, Section 1.4 (Study Rationale), Section 3.0 (Patient Eligibility), and Section 10.0 (Statistical	Listed an accrual goal of 32 evaluable subjects	Updates to an accrual goal of 20 evaluable subjects and provides a new statistical plan in Section 10.0.	The study has been slow to accrue, and reducing the sample size will increase the feasibility of completing the trial in a timely manner.		

Considerations)			Modification requested by the lead site after receiving support from Celgene to reduce sample size.
Section 4.0 (Treatment Plan)	N/A	Adds the following: With PI approval, dose modifications (interruptions and reductions) may be permitted for any grade AE deemed intolerable by the patient, or per treating investigator discretion (with PI approval) if thought to be in the best interest of the patient.	Modification requested by the DSMC to align with best interests of participating patients.
Section 4.6 (Patient Replacement)	Stated: Any patient who completes fewer than 2 total cycles of therapy and is withdrawn for any reason except POD or toxicity will still be considered evaluable for toxicity endpoints; however, for the purpose of efficacy endpoints, another patient may be added to the accrual goal with the approval of the Data and Safety Monitoring Committee (DSMC) at NU.	Updates language to include the bolded text: Any patient who completes fewer than 2 total cycles of therapy and is withdrawn for any reason except POD or toxicity will still be considered evaluable for toxicity endpoints but will not be evaluable for efficacy endpoints ; for the purpose of efficacy endpoints, another patient may be added to the accrual goal with the approval of the Data and Safety Monitoring Committee (DSMC) at NU.	Language clarification requested by the Quality Assurance Monitor to clarify replacement of non- evaluable patients
